	
diagnosed with septic shock, fluid resuscitation should be performed according to the routine diagnosis and treatment. 4 The legal guardian has signed the informed consent.

	
excluded criteria:
 
1 combined with neurogenic shock, trauma and hemorrhagic shock; 2 symptomatic patent ductus arteriosus; 3 combined with congenital heart disease; 4 give up treatment or death within 24 hours of admission; 5 The legal guardian refused to participate in the study; 6 Key information and information missing.

Treatment plan	
This study was an observational study. Clinicians developed a diagnosis and treatment plan based on the treatment plan for neonatal sepsis in the sixth edition of " Practical Neonatology " and the " International Guidelines for the 2020 Saving Sepsis Campaign: Management of Septic Shock and Sepsis-related Organ Dysfunction in Children. "

efficacy evaluation	
The main efficacy indicators: hospitalization time and cumulative hospitalization time, mortality.
 
Secondary efficacy indicators: cumulative fluid volume during fluid resuscitation, use of vasoactive drugs and mechanical auxiliary gas.

	
Safety evaluation index: Mortality.

statistical method	
Measurement data and count data were expressed as mean \pm standard deviation [or median (interquartile range)] and percentage (%), respectively. Normal and non-normal distribution data were analyzed by two independent sample t test and Mann-Whitney U test, respectively. The chi-square test was used to compare the count data rates between groups. Kaplan-Meier

	
method was used to draw the survival curve, and Log-rank test was used to compare the difference of 28-day cumulative survival rate between the two groups. Baseline covariates were adjusted in the Cox proportional hazards model to calculate the hazard ratios (HRs) and their 95 % confidence intervals. Logarithmic conversion was performed on hospital stay and organ support time and linear regression analysis was used to calculate a 95 % confidence interval for reporting. No data with missing information is interpolated. The above statistical analysis was performed using R software, and the test was bilateral, and $p < 0.05$ was considered statistically significant.

Research period
	
January 1, 2022 – December 31, 2023

一、 Research background

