excessive lung water volume load should be considered. Increases should begin to make adjustments in fluid therapy and respiratory therapy that are most suitable for patients [28]. However, previous studies are basically aimed at adults, and the number of studies in neonates is very limited. In clinical studies, due to the particularity of neonatal anatomy and physiology, there is a lack of research on the application of severe ultrasound technology in fluid resuscitation of neonatal septic shock. [29] There is an urgent need for an effective non-invasive monitoring method to assist fluid resuscitation in children with septic shock.

At present, the fluid resuscitation methods used in our department for neonates with septic shock mainly include : conventional fluid resuscitation, severe ultrasound-guided fluid resuscitation and NICOM-assisted fluid resuscitation. In this prospective observational study, children with neonatal septic shock diagnosed in the neonatal intensive care unit of Guangdong Second People 's Hospital from January 1,2022 to December 31,2023 were included in the study. According to the different monitoring methods used in shock treatment, 30 cases of severe ultrasound-assisted fluid resuscitation, 30 cases of NICOM-assisted fluid resuscitation and 30 cases of conventional fluid resuscitation were collected, a total of 90 cases. The hemodynamic differences, NICU hospitalization time, renal replacement therapy / mechanical ventilation, and 28-day mortality were compared among the three groups to comprehensively evaluate the application value of cardiopulmonary ultrasound and non-invasive cardiac output in fluid resuscitation of neonatal septic shock. Improve the therapeutic effect of neonatal septic shock, enrich the application field of clinical ultrasound, and promote the cross-fusion of ultrasound and pediatrics, and provide clinical basis for subsequent prospective studies.

二、 research objective

1. Main Objective: To study the application value of severe ultrasound and non-invasive cardiac output technique in fluid resuscitation of neonatal septic shock.

2.Secondary purpose: To promote the therapeutic effect of neonatal septic shock and enrich the application field of clinical ultrasound technology.

三、 Research Design Types, Principles, and Test Procedures

1. Research Design

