In this study, children with neonatal septic shock diagnosed in the neonatal intensive care unit of the Second People 's Hospital of Guangdong Province from January 1,2022 to December 31,2023 were included. According to the different monitoring methods used in routine / clinical shock treatment, 30 cases of severe ultrasound-assisted fluid resuscitation, 30 cases of NICOM-assisted fluid resuscitation and 30 cases of routine fluid resuscitation were collected. The demographic data, blood examination and microbiological examination data of the three groups at admission were collected. The fluid volume, blood lactic acid, blood pressure, vasoactive drugs (such as dopamine and epinephrine / norepinephrine), mechanical ventilation, renal replacement therapy and antibiotic use before fluid resuscitation were collected. The cumulative fluid infusion volume during fluid resuscitation (6 hours), and the use of vasoactive drugs and mechanical ventilation for 6 hours were collected. NICU hospitalization time, cumulative hospitalization time and mortality were collected.

四、 case selection

1. Inclusion criteria:

1 Born less than 28 days on admission; 2 Conform to the diagnostic criteria for neonatal septic shock in the ' 2020 International Guidelines for Saving Sepsis Campaign: Management of Septic Shock and Sepsis-related Organ Dysfunction in Children; 3 For children diagnosed with septic shock, fluid resuscitation should be performed according to the routine diagnosis and treatment. 4 The legal guardian has signed the informed consent.

2. excluded criteria:

1 combined with neurogenic shock, trauma and hemorrhagic shock; 2 symptomatic patent ductus arteriosus; 3 combined with congenital heart disease; 4 give up treatment or death within 24 hours of admission; 5 The legal guardian refused to participate in the study; 6 Key information and information missing.

3. Elimination criteria

Subjects who have been enrolled in the study but meet one of the following criteria should be excluded :

(1) After inclusion, those who did not meet the inclusion criteria or met the exclusion criteria were found.

(2) Those who have not used test drugs / interventions.

4. Standard for suspension of research

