(3) The cumulative fluid infusion volume during fluid resuscitation (6 hours), and the use of vasoactive drugs and mechanical ventilation for 6 hours were collected.

(4) NICU hospitalization time, cumulative hospitalization time and mortality were collected.

七、 standards for efficacy appraisal

The main efficacy criteria : NICU hospitalization time and cumulative hospitalization time, mortality.

Secondary efficacy criteria : cumulative fluid volume during fluid resuscitation (6 hours), and use of vasoactive drugs and mechanical ventilation for 6 hours.

八、 Observation of adverse events

Observation of adverse events : Clinicians should evaluate the fluid resuscitation of children at any time during the experiment. If the clinical symptoms and other auxiliary examinations (such as heart rate, liver size, mental state, X-ray, blood gas analysis, etc.) are

inconsistent with the relevant non-invasive examinations, the experiment should be terminated immediately and the superior physician should be found in time to assist.

九、 Data security monitoring

Clinical research will develop a corresponding data security monitoring plan based on the size of the risk. All adverse events were recorded in detail, properly handled and tracked until they were properly resolved or stable. Serious adverse events and unexpected events were reported to the ethics committee, competent authorities, sponsors and drug supervision and management departments in a timely manner according to the regulations. The main researchers regularly conduct a cumulative review of all adverse events, and if necessary, convene a meeting of researchers to assess the risks and benefits of the study ; research that is greater than the minimum risk will arrange independent data monitors to monitor the research data, and high-risk research will establish an independent data security supervisory committee to monitor the accumulated security data and effectiveness data to make recommendations on whether the research will continue.

十、 Statistical processing

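### Excluding infants who die or give up treatment within 24 hours of admission selects the mortality analysis population on its own outcome

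*Combined protocol and SAP*

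**What the plan says.** Item 4 of the exclusion criteria (Section 四, 2, and the Abstract under case selection) is "give up treatment or death within 24 hours of admission". Section 四, 3 then carries the exclusions past enrolment. Its lead-in reads "Subjects who have been enrolled in the study but meet one of the following criteria should be excluded", and its first criterion is "After inclusion, those who did not meet the inclusion criteria or met the exclusion criteria were found".

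The event named in item 4 is also an endpoint:

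- Section 七: "The main efficacy criteria : NICU hospitalization time and cumulative hospitalization time, mortality".
- Abstract, efficacy evaluation: "Safety evaluation index: Mortality". No other safety index is listed.
- Section 一, last paragraph: "28-day mortality were compared among the three groups".
- Section 十 analyses 28-day survival by Kaplan-Meier curves, the log-rank test and a Cox model. It names no time origin, analysis set, landmark or sensitivity analysis.

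Groups are not randomised. They are formed "According to the different monitoring methods used in routine / clinical shock treatment" (Section 三, 1). The same section sets the resuscitation period under study at six hours.

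**The concern.** Whether an infant dies in the first day cannot be known at screening. In a prospective study with signed consent, an infant can be enrolled, resuscitated, die, and then be taken out of the comparison because of that death. Two things are at stake.

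First, the reported mortality would no longer be mortality after resuscitation. It would describe only infants who got past the first 24 hours in hospital without dying or giving up treatment.

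Second, the clock runs from admission, not from shock or resuscitation. Two infants who die equally soon after resuscitation are kept or dropped according to when shock began. Without randomisation, nothing makes the early share of deaths, or the time from admission to shock, alike across the three groups. Any effect of monitoring on deaths inside the window is hidden. Covariate adjustment in the Cox model cannot recover infants who are no longer in the data.

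**Working it through.** The plan gives no figure for early deaths, so there is none to reproduce. Its only related figure, 3 × 30 = 90, is consistent and not in dispute.

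**Inputs.** From the documents: 30 infants per group (Abstract); background in-hospital mortality above 40%, and a peak of 71% below 1000 g (Section 一); six-hour resuscitation (Section 三, 1). Assumed: 40% as 28-day mortality, 30% as a lower value, and every share or count of removed infants.

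**1. Which deaths are reached.** If resuscitation starts u hours after admission, deaths in the next max(0, 24 − u) hours are removed: 24 h for u = 0, 12 h for u = 12, none for u ≥ 24. The whole six-hour resuscitation lies inside the window when u ≤ 24 − 6 = 18.

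**2. Absolute mortality, deaths alone removed.** With true mortality m and a share e of deaths removed, observed mortality is m(1 − e)/(1 − m·e).

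| m | e = 0.1 | e = 0.2 | e = 0.4 |
|---|---|---|---|
| 0.30 | – | 25.5% | 20.5% |
| 0.40 | 37.5% | 34.8% | 28.6% |
| 0.71 | – | 66.2% | 59.5% |

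For example, at m = 0.40 and e = 0.2: 0.32/0.92 = 34.8%. The documents do not say whether removed infants are replaced. Refilling to 30 would not repair the rate: 30 × 0.348 = 10.4 or 30 × 0.286 = 8.6 expected deaths, against 12.

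**3. Infants who give up treatment.** Item 4 removes these too. Take 12 deaths in 30 (40%) and remove one death and three infants who gave up but are alive: 11/26 = 42.3%. The reading now lies above the truth.

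**4. No true difference.** Take 12/30 deaths in both groups. Removing 2 early deaths from one and 4 from the other gives 10/28 = 35.7% against 8/26 = 30.8%, a spurious 4.9 points that favours the group with more early deaths. The sign reverses if the counts are swapped, and removing 3 from each gives 0.

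For scale, the standard error of the difference at 40% is √(2 × 0.4 × 0.6/30) = 12.6 points, with a 95% half-width of 1.96 × 12.6 = 24.8 points. The standard error for 10/28 against 8/26 is 12.8 points, so the shift is 4.9/12.8, about 0.39 standard errors. If that shift were systematic, a normal-approximation two-proportion test at two-sided 5% would reject about 6.7% of the time. This is not the planned log-rank test.

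**5. A true difference.** Take 8/30 against 12/30, that is −13.3 points, with 2 early deaths in each group and k of the 4 excess deaths also early. The first group reads (8 − 2)/28 = 21.4%.

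| k | Second group reads | Observed difference |
|---|---|---|
| 0 | 10/28 = 35.7% | −14.3 points |
| 2 | 8/26 = 30.8% | −9.3 points |
| 4 | 6/24 = 25.0% | −3.6 points |

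An effect that acts mainly on early deaths would be largely lost from the comparison.

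**The case against.** Four objections carry weight.

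- **The size is not established.** No section gives the timing of shock or death. If most shock begins more than 24 hours after admission, few deaths are touched. The null example is a fraction of one standard error, and 2 against 4 removals in a single study could be chance, which is not bias. This stands: the examples show mechanism, not expected harm.
- **The direction is not fixed.** A reader might infer that the rule always understates mortality. It does so only when deaths alone are removed; step 3 shows the opposite. A reader might also infer that it favours one monitoring method. The documents give nothing on which group would have more early deaths.
- **Removal after enrolment may never occur.** Section 十一 requires consent before selection, but no section says how soon after admission enrolment takes place. If eligibility is settled at or after 24 hours, item 4 acts as a screen and the elimination criterion removes nobody under it. This stands as to the route. The population is still selected on the outcome, so the phrase must also leave the eligibility list.
- **The rule may be meant for moribund or never-resuscitated infants.** Limiting the analysis set to infants who start resuscitation already omits the latter. Lactate, blood pressure, vasoactive drugs and ventilation before resuscitation are collected (Section 三, 1) and can be used for adjustment.

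Nor should a reader infer that these deaths vanish from adverse-event reporting. Section 九 provides for that separately.

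**Conclusion.** The point holds as a flaw in the analysis population. As written, the plan conditions a main efficacy criterion, the only safety index and the 28-day survival analysis on the outcome itself, and nothing restores the infants removed. Confidence in that is high, because it rests on the wording.

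Confidence in the size is low. Under the assumptions shown, a true 40% reads as 28.6% to 37.5% when 10% to 40% of deaths are removed. A null comparison can show a spurious difference of about 5 points, and a true difference of 13.3 points can shrink to 3.6. The last case requires all four excess deaths to be early. Bias in the comparison requires that the early share of deaths, or the time from admission to shock, differ systematically by group. The documents neither show this nor rule it out, and they do not support the stronger conclusion that the mortality comparison will be materially wrong.

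The suspension and exit rules, and missing six-hour data, are separate matters and add nothing to this point.

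**What to change.** - Delete the 24-hour phrase both from the exclusion criteria (Abstract and Section 四, 2) and as a ground for removal after enrolment. Changing only one leaves the selection in place.
- In Section 十, define the mortality set as all consented eligible infants who start fluid resuscitation, with time zero at that start. Count deaths within 24 hours of admission as events.
- Assign the monitoring group by a rule set in advance that does not depend on survival, for example the method chosen at the start of resuscitation. Record later changes, and add a sensitivity analysis by method actually used.
- For infants who give up treatment, use day-28 vital status where obtainable. Otherwise censor at last contact, with a sensitivity analysis that counts them as deaths, since this censoring is probably informative.
- Report the present restricted set as a sensitivity analysis. List removals by group and reason, and give the number who died before consent; these remain outside the set and should be stated as a limitation.

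The cost is mainly wording. No post-discharge follow-up is listed in Section 六, so day-28 status for infants who leave may need added data collection. Fixing the group at the start may dilute or misclassify groups when the method changes, to an extent the documents do not allow one to judge. Early deaths shorten stay, so the two length-of-stay outcomes need a stated rule for deaths; deaths after 24 hours already require one.

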At present, non-invasive monitoring and inspection methods have broad application prospects in the field of fluid management of septic shock. Monitoring cardiac output in the ICU has become part of routine patient management, helping doctors assess patients ' clinical status and track their response to various interventions. Non-invasive cardiac output monitoring (NICOM) is a non-invasive cardiac output detection method that detects hemodynamic indicators by bioelectrical impedance method. NICOM can dynamically and conveniently detect the hemodynamic characteristics of patients on a non-invasive basis in real time. In recent years, NICOM has been gradually applied in pediatric NICU, especially in the treatment of neonatal septic shock patients, and has achieved certain results [24]. In addition, among various monitoring methods, ultrasound technology can provide cardiovascular system-related information from both functional and structural aspects, and is an important tool for hemodynamic monitoring in adult patients with septic shock [25]. More and more evidence shows that severe ultrasound-guided fluid resuscitation can improve the prognosis of critically ill patients, and was written into the 2015 ' Severe Hemodynamic Therapy-Beijing Consensus ' [26]. Ultrasound technology has the characteristics of non-invasive, real-time and repeatable, and integrates structural and functional assessment, problem goal orientation, quantitative and qualitative combination, dynamic assessment of volume status (cardiac function), volume responsiveness (inferior vena cava diameter) and organ function changes (lung ultrasound), so as to timely and accurately guide fluid resuscitation and positive inotropic drug use. It is an ideal medical tool for hemodynamic management in patients with septic shock and has been integrated into the diagnosis and treatment of adult septic shock [25, 27]. In particular, ultrasound diagnosis of pulmonary edema depends on the discovery of characteristic B lines, and has a high consistency with CT diagnosis. If the patient 's B line under lung ultrasound monitoring is significantly increased, suggesting increased lung water, increased lung permeability, such as reduced cardiac function and inferior vena cava dilatation, at this time, the presence of

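### Eliminating enrolled infants when a cardiac lesion comes to light, with no common cardiac assessment, may remove more of them from the ultrasound group and bias the mortality comparison

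*Combined protocol and SAP*

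**What the plan says.** Under case selection, the elimination criteria open with "Subjects who have been enrolled in the study but meet one of the following criteria should be excluded". Item (1) then reads "After inclusion, those who did not meet the inclusion criteria or met the exclusion criteria were found". No time limit is given, and nothing says which source of diagnosis counts.

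The exclusion criteria that this reopens include "2 symptomatic patent ductus arteriosus; 3 combined with congenital heart disease". The first needs symptoms; the second has no such qualifier.

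On the three methods, the Research background says that "ultrasound technology can provide cardiovascular system-related information from both functional and structural aspects", and the study outline at its end states the aim to "comprehensively evaluate the application value of cardiopulmonary ultrasound and non-invasive cardiac output". Of NICOM it says that the method "detects hemodynamic indicators by bioelectrical impedance method". It describes no imaging as part of conventional resuscitation. Groups are formed by the monitoring method used, not by randomisation.

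The observation items list demographic, blood and microbiology data at admission for all three groups, but no echocardiogram and no PDA or heart disease status. No section says how or when these conditions are ruled out. The statistical section defines no analysis set that keeps eliminated infants and no sensitivity analysis for them. Mortality is one of the main efficacy criteria, beside NICU stay and cumulative hospital stay.

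**The concern.** The monitoring method defines the group, and one of the three methods may itself reveal a reason to remove the infant. If a heart lesion is more likely to be seen in the ultrasound group, an infant there can be eliminated while an identical infant in another group stays in the analysis. Membership of the analysed group would then depend on both exposure and prognosis.

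If infants with these lesions die more often, the ultrasound group would show lower mortality with no true effect. The planned Cox adjustment for baseline covariates could not correct this, because a lesion that was not looked for in a group cannot be adjusted for there. The plan does not say whether eliminated infants are replaced to reach 30 per group; replacement would not undo the selection.

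**Working it through.** **The plan's own figures.** There is no plan figure to reproduce on this point. The sample size is only 3 × 30 = 90, with no stated effect size or power. With 30 per group, one death is 1/30 = 3.3 percentage points.

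**The route to bias.** It needs three things:
1. A rule that removes infants after enrolment. This is stated.
2. Unequal chances of detection. The descriptions of the methods make this possible, but it is not shown.
3. Different prognosis in the infants removed. This is plausible, but the documents do not quantify it.

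**Illustration of size, with no true effect of monitoring.** Mortality among infants retained in a group is

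M = [p(1−d)·m1 + (1−p)·m0] / [p(1−d) + (1−p)]

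where p is the share of enrolled infants with an unrecognised lesion that meets exclusion 2 or 3, d the share of those detected and eliminated, and m1 and m0 mortality with and without a lesion.

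All inputs are assumptions: m1 = 0.60, m0 = 0.35, p = 0.10 to 0.30. At p = 0.20, overall mortality before elimination is 0.20 × 0.60 + 0.80 × 0.35 = 0.40, which is of the order of the in-hospital figure of more than 40% quoted in the Research background.

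Detection 90% with ultrasound v 40% elsewhere:
- p = 0.10: ultrasound (0.006 + 0.315)/0.91 = 0.3527; others (0.036 + 0.315)/0.96 = 0.3656. Difference 1.3 points, or 30 × 0.0129 = 0.4 deaths per 30.
- p = 0.20: ultrasound (0.012 + 0.280)/0.82 = 0.3561; others (0.072 + 0.280)/0.92 = 0.3826. Difference 2.65 points, or 30 × 0.0265 = 0.8 deaths per 30. Per 30 enrolled, 30 × 0.20 × 0.90 = 5.4 infants are eliminated with ultrasound and 30 × 0.20 × 0.40 = 2.4 elsewhere.
- p = 0.30: ultrasound 0.263/0.73 = 0.3603; others 0.353/0.88 = 0.4011. Difference 4.1 points.

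Extreme detection, 100% v 0%, a bound for these prevalences and mortalities:
- p = 0.20: 0.350 v 0.400, or 5.0 points.
- p = 0.30: 0.350 v 0.425, or 7.5 points.

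Equal detection, 90% in every group at p = 0.20: 0.356 v 0.356, or 0 points. If m1 = m0, the difference is also 0 whatever the detection rates.

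**A second set of assumptions.** With m0 = 0.40, m1 = 0.60 to 0.71, p = 5% to 30%, and detection 90% with ultrasound v 0 to 60% elsewhere, the difference runs from 0.3 to 8.0 points; with 100% v 0% it reaches 9.3. The 71% is the figure the Research background quotes for a different high-risk group, infants under 1000 g, so it serves only as a high value.

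**Length of stay.** No direction can be derived. Removing infants with long stays would shorten the group's average, but removing infants who die early would lengthen it.

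**The case against.** Several counter-arguments have force:

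- **Unequal removal is an inference.** A reader might conclude that the ultrasound group is in fact cleared of high-risk infants. The documents do not show that. They nowhere say that infants in the NICOM or conventional groups go without echocardiography. The observation items are study variables, not an eligibility work-up, so their silence on cardiac imaging is weak evidence. Both exclusions apply to all groups at entry.
- **PDA must be symptomatic.** A duct merely seen on a scan does not meet the criterion, and symptoms can be observed in every group. This narrows the route mainly to congenital heart disease, plus PDA whose symptoms were first attributed to sepsis.
- **The open-ended rule applies to every group.** A lesion found later in a NICOM or conventional infant also leads to elimination, so zero detection in those groups is an extreme.
- **The scan is not specified.** Cardiac imaging is described in the background, no methods section gives views or timing, and the abstract's title field names lung ultrasound only. The cardiopulmonary wording and the mention of structural information make heart imaging likely, but a scan able to diagnose congenital heart disease is not established.
- **The sizes are assumed.** A prevalence of 20% unrecognised lesions, after cardiac exclusions at entry, has no support in the documents.

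All of this limits how strongly the point can be put and how large the bias may be. It does not remove the gap. Item (1) expressly provides for exclusions found after inclusion, nothing makes the chance of finding them alike across groups, and bias needs only unequal detection, not absent detection.

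**Conclusion.** The point holds as a risk that the plan creates and leaves unaddressed. The elimination rule, joined to an exposure that may itself reveal an exclusion, allows the monitoring method to influence who is analysed. If detection is higher with ultrasound and affected infants do worse, the mortality comparison is biased towards ultrasound.

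The size is likely to be modest: about 1.3 to 2.65 points (0.4 to 0.8 deaths per 30) at 10–20% prevalence, mortality 60% v 35% and detection 90% v 40%. The 5 and 7.5 point figures are upper bounds on detection, not expectations. Every one of these inputs is assumed.

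A reader might also infer that all three main outcomes are tilted towards ultrasound. That is not supported: only mortality has a predictable direction, because death shortens NICU and hospital stay.

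Severity: should-fix. Confidence: moderate.

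**What to change.** - Apply exclusions 2 and 3 in all three groups only on information available before fluid resuscitation started, and not on findings of the study monitoring method. State which sources count.
- Amend elimination item (1) so that a lesion first found afterwards does not remove the infant from the main analysis.
- Record when and how each lesion was found.
- Report late-found lesions, and all eliminations, by group and reason.
- Treat any analysis without late-found cases as secondary, and say that it carries the same differential-detection bias.

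At p = 0.20 in the illustration, keeping every enrolled infant gives 40.0% in each group, a difference of 0.

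The cost is a short revision of the eligibility and elimination text, a definition of the admissible pre-resuscitation sources, and a few data fields. The downside is that a few infants with a late-found lesion stay in, so the population is slightly less pure. The change concerns eligibility and analysis only, not clinical care.
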